15 AUDITING

As coordinating center of this trial, Washington University (via the Quality Assurance and Safety Monitoring Committee (QASMC)) will monitor each participating site to ensure that all protocol requirements are being met; that applicable federal regulations are being followed; and that best practices for patient safety and data collection are being followed per protocol. Participating sites will be asked to send copies of all audit materials, including source documentation. The audit notification will be sent to the Washington University Research Patient Coordinator, who will obtain the audit materials from the participating institution.

Notification of an upcoming audit will be sent to the research team one month ahead of the audit. Once accrual numbers are confirmed, and approximately 30 days prior to the audit, a list of the cases selected for review (up to 10 for each site) will be sent to the research team. However, if during the audit the need arises to review cases not initially selected, the research team will be asked to provide the additional charts within two working days.

Items to be evaluated include:

- Subject screening and enrollment
- Reporting of adverse events
- Maintenance of HIPAA compliance
- Completeness of regulatory documentation
- Completeness of participant documentation
- Acquisition of informed consent
- IRB documentation
- Issues of protocol adherence

Additional details regarding the auditing policies and procedures can be found at <https://siteman.wustl.edu/wp-content/uploads/2015/10/QASMC-Policies-and-Procedures-03.31.2015.pdf>

16 STATISTICAL CONSIDERATIONS

16.1 Study Objectives and Endpoints

Primary Objective:

Demonstrate that sequential short course radiotherapy followed by 8 cycles of multi-drug chemotherapy will elicit a rate of significant clinical response to allow an organ preservation approach for at least 30% (6/20) patients at 1 year.

Secondary Objectives

1. Obtain prospective patient reported outcomes from an organ preservation approach for early stage rectal cancer.
2. Determine the incidence of any grade ≥ 3 toxicity during treatment.
3. Determine the incidence of post chemoradiotherapy grade ≥ 3 toxicity at 1 year
4. Determine quality of anorectal function at 1 year by FACT-C

16.2 Study Design and Sample Size Justification

This pilot study is designed to demonstrate proof of concept for an organ preservation strategy applied to a low risk rectal cancer cohort. As such, the sample size is not determined by traditional power calculations, but rather by clinical judgment – if organ preservation is not possible in 30% of this initial cohort (6/20 patients), then the strategy will be abandoned. If at least 30% of patients at 1 year may be treated with organ preservation, then the concept may proceed to a separate phase II approach.

16.3 Interim Analyses and Stopping Rules

An interim analysis will be performed on the primary endpoint once 10 subjects have been enrolled and have completed the evaluation after chemotherapy. There will be possible early stopping if less than 2/10 of the initial patients enrolled who complete radiotherapy and chemotherapy remain potential candidates for organ preservation.

16.4 Definition of Evaluability

Patients who have completed all radiotherapy and chemotherapy will be considered evaluable for analysis. Patients who are inevaluable for the primary endpoint will be replaced.

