8 DOSE DELAYS/DOSE MODIFICATIONS

Radiotherapy for this trial may take place over a maximum of 10 business days before it is considered a protocol deviation. There are no dose adjustments (reductions, omissions) associated with radiotherapy.

All toxicities should be graded according to the Common Terminology Criteria for Adverse Events (CTCAE), version 4.0. Dose modifications are based upon dose level administered at last treatment day. If the dose level has been reduced due to toxicity, re-escalation is not permitted. If dose reduction is required after dose level -3, patient will discontinue protocol therapy.

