8.2 Dose Modifications for Toxicity Related to FOLFOX and CapeOx

The provided dose modifications are strongly recommended. However, out of consideration of unforeseen clinical scenarios, dose modifications during FOLFOX chemotherapy are ultimately at the discretion of the primary treating provider. The use of 5-FU bolus is at the discretion of the treating physician. Modifications should be reported to the research coordinator. Refer to table 8.2 and 8.3 for guidance regarding suggested dose reductions and treatment delays, consistent with best oncologic practices.

Toxicity NCI Grade (Value)	Worst interval toxicity	Day of treatment
Neutropenia (ANC)		
Grade 1 (ANC < LLN – 1500/mm ³)	Maintain dose level	If ANC < 1000 on day of treatment, hold and check weekly until ≥ 1000 mm ³ . Then treat based on interval toxicity. If ANC < 1000 after 4 weeks, discontinue therapy.
Grade 2 (ANC < 1499 – 1000/mm ³)		
Grade 3 (ANC < 999 – 500/mm ³)	Reduce 1 dose level	
Grade 4 (ANC < 500/mm ³)		
Thrombocytopenia		
Grade 1 (PLT < LLN – 75,000/mm ³)	Maintain dose level	If PLT < 75,000 on day of treatment, hold and check weekly until ≥ 75,000 mm ³ . Then treat based on interval toxicity. If PLT < 75,000 after 4 weeks, discontinue therapy.
Grade 2 (PLT 74,999 – 50,000/mm ³)		
Grade 3 (PLT 49,999 – 25,000/mm ³)	Reduce 1 dose level	
Grade 4 (PLT < 25,000/mm ³)		
Diarrhea		
Grade 1	Maintain dose level	Hold chemotherapy if any grade of diarrhea above grade 1 is present with the patient not taking antidiarrheal agents within 24 hours of treatment. Reduce 5-FU and oxaliplatin 1 dose level upon resolution of diarrhea. If diarrhea has not resolved within 4 weeks of scheduled treatment day, discontinue therapy.
Grade 2		
Grade 3		
Grade 4		
Other nonhematologic toxicities (except neurologic, alopecia, anorexia, nausea/vomiting if can be controlled by antiemetics)		
Grade 1	Maintain dose level	Maintain dose level
Grade 2		
Grade 3	Reduce 1 dose level	Hold until resolved to grade ≤1. Reduce 5-FU and oxaliplatin 1 dose level
Grade 4		

8.3 Dose Modifications for Neurologic Toxicity (Paresthesia or Dysesthesia) Related to Oxaliplatin

Grade	Duration of Toxicity		
	1 – 7 Days	> 7 Days	Persistent Between Doses
Grade 1 Short duration that resolves and does not interfere with function	No change	No change	No change
Grade 2 Interfering with function, but not activities of daily living (ADL)	No change	No change	Reduce oxaliplatin 1 dose level

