Grade 3 With pain or with functional impairment that also interferes with ADL	1 st time: reduce oxaliplatin 1 dose level	1 st time: reduce oxaliplatin 1 dose level	Discontinue oxaliplatin
	2 nd time: reduce oxaliplatin another dose level	2 nd time: reduce oxaliplatin another dose level	
Grade 4 Persistent symptoms that are disabling or life-threatening	Discontinue oxaliplatin	Discontinue oxaliplatin	Discontinue oxaliplatin

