16.6 Accrual

Assuming 10% inevaluable cases, the overall accrual will be 22 patients. The rate of accrual for the study is expected to be about 8 patients per year. It is expected that the accrual period of the study will be completed in about 3 years.

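### Counting only patients who complete all treatment, and replacing the rest, can bias the 6/20 organ-preservation decision upward, modestly at the plan's own 10% inevaluable rate

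*Combined protocol and SAP*

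**What the plan says.** Section 16.4 defines the analysis population: "Patients who have completed all radiotherapy and chemotherapy will be considered evaluable for analysis". It continues: "Patients who are inevaluable for the primary endpoint will be replaced".

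Section 16.2 sets the decision: "if organ preservation is not possible in 30% of this initial cohort (6/20 patients), then the strategy will be abandoned". It does not mention completion of treatment.

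Section 16.3 allows possible early stopping if "less than 2/10 of the initial patients enrolled who complete radiotherapy and chemotherapy remain potential candidates for organ preservation".

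Section 16.6 links enrolment to the analysed number: "Assuming 10% inevaluable cases, the overall accrual will be 22 patients".

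Section 16.5 promises descriptive statistics and the incidence of organ preservation. It names no analysis of all treated patients and does not say how early stoppers are classified.

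Section 8 describes how treatment can end early. One rule is firm: "If dose reduction is required after dose level -3, patient will discontinue protocol therapy". The table in 8.2 adds stops for slow recovery, for example "If ANC < 1000 after 4 weeks, discontinue therapy", with similar entries for platelets and diarrhea. The text above that table presents it as strongly recommended guidance and leaves modifications to the treating provider. The neurotoxicity table in 8.3 has entries that stop one drug only: "Discontinue oxaliplatin".

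**The concern.** Whether a patient counts toward the go/no-go decision depends on something that happens after enrolment and can be caused by the treatment. A patient who stops for toxicity leaves the denominator, and someone who got through the full sequence takes the place. If early stoppers keep the organ less often than completers, the observed rate overstates what the strategy delivers to those who start it, and both the abandon rule and the interim criterion are met too rarely. If early stoppers do equally well, there is no bias.

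The abandon rule is the one firmly worded decision in section 16, so its denominator matters most. Two further gaps make it hard to apply. Section 16.4 does not say whether a course with reduced doses, or with oxaliplatin alone discontinued, counts as completed. Section 5.3 schedules the response assessment only after completion of chemotherapy, so an early stopper has no specified classification.

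**Working it through.** **Plan's own figure.** 20 × 1.10 = 22, as stated in 16.6. (20/0.90 = 22.2, or 23 rounded up; the difference is immaterial here.) The 20 itself rests on clinical judgment (16.2), so there is no power calculation to reproduce.

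**Same successes, two denominators.** 6/20 = 30.0%; 6/22 = 27.3%. Six successes meet the 30% line among 20 completers but not among the planned 22.

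**Inputs.** Final cut-off 6/20 (16.2); interim criterion fewer than 2/10 (16.3); inevaluable share 10% (16.6). Assumptions, because the plan gives no figures: the true preservation rate p among all treated patients, and the rate r among early stoppers. Let f be the share of treated patients who stop early. Setting f = 0.10 assigns the whole inevaluable allowance to early stoppers and so gives an upper figure.

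**Formula.** Completer rate pc = (p − f·r)/(1 − f). The chances are exact binomial: P(X ≥ 6 | 20) for proceeding, P(X < 2 | 10) for the interim criterion.

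**Results at p = 0.20, f = 0.10.**

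| Population | Rate | P(≥ 6/20) | P(< 2/10) |
|---|---|---|---|
| All treated | 0.200 | 0.196 | 0.376 |
| Completers, r = 0.10 | (0.20 − 0.01)/0.90 = 0.211 | 0.234 | 0.343 |
| Completers, r = 0 | 0.20/0.90 = 0.222 | 0.274 | 0.312 |

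The excess chance of proceeding is 0.234 − 0.196 = 0.038 to 0.274 − 0.196 = 0.078.

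**If half of the 10% never start (f = 0.05, r = 0).** pc = 0.20/0.95 = 0.2105 and P(≥ 6/20) = 0.232, an excess of about 0.036. The interim difference falls from 0.063 to about 0.031.

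**Other true rates, f = 0.10, r = 0** (completers minus all treated, P(≥ 6/20)):
- p = 0.10: 0.0184 − 0.0113 = 0.007
- p = 0.15: 0.1018 − 0.0673 = 0.035
- p = 0.25: 0.4959 − 0.3828 = 0.113
- p = 0.30: 0.7028 − 0.5836 = 0.119
- p = 0.35: 0.8524 − 0.7546 = 0.098

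**Effect of the fix when documentation is missing.** Suppose r = 0.10 and no early stopper has a documented response.
- Interim, p = 0.20: counted rate 0.20 − 0.10 × 0.10 = 0.19, so P(< 2/10) = 0.407, against 0.343 among completers and 0.376 if every status were known.
- Final, p = 0.30: the chance of proceeding is 0.584 with every status known, against 0.665 (r = 0.10, pc = 0.322) to 0.703 (r = 0) among completers. With r = 0.10 and none documented, the counted rate is 0.29 and the chance is 0.545.

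**The case against.** The strongest reply is that a completers' question is a defensible choice for a pilot. The objective concerns radiotherapy followed by 8 cycles, section 2 does not expect proof, interim stopping is only possible, and success only means that the concept may proceed. This stands, and it limits the severity. It does not remove the need to know what happened to patients who started and could not finish.

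A reader might infer four stronger things that the documents do not support.

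- **That 16.2 and 16.4 flatly contradict each other.** They need not. Read with 16.6, the cohort of 20 can mean 20 evaluable patients, and calling it initial may only contrast the pilot with the later phase II study. The fault is that 16.2 leaves this unsaid.
- **That 16.3 also drops and replaces non-completers.** It contains no replacement rule. It can mean ten completers, or ten enrolled patients of whom only completers can be candidates, in which case early stoppers already count against the strategy. Its opening sentence leans toward the first reading but does not settle it.
- **That the protocol mandates every toxicity stop.** Only the rule after dose level −3 is firm; the 8.2 stops are discretionary guidance.
- **That poor responders are removed.** They are not. Patients who complete treatment without a complete response stay in the denominator.

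Assigning all of the 10% to early stoppers is also an upper bound, since 16.6 gives no reasons for inevaluability.

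**Conclusion.** The point holds in a limited form. Section 16.4 conditions the primary endpoint on completing treatment and replaces the others, non-completion can be caused by the treatment, and nothing in 16.5 corrects for it. The bias is upward if early stoppers do worse than completers and absent if they do equally well; the documents give no data on which applies. At the plan's 10% and an assumed true rate of 20%, the chance of reaching 6/20 rises from 0.196 to between 0.234 and 0.274, less if part of the 10% never start. That is modest, but it bears on the plan's one firm decision, and 16.2 and 16.3 each leave their denominator open to two readings. It should be fixed; it does not invalidate the pilot.

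**What to change.** Reword 16.2 to 16.5 as follows.

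- **Final decision.** Apply 6/20 to the first 20 patients who start radiotherapy. Replace only those who never start.
- **Early stoppers.** Count one as a success only if organ preservation is documented by the criteria used for completers; otherwise count as not preserved. Absence of recorded surgery is not enough, because completers are judged on clinical complete response. Add a sensitivity analysis for unknown status.
- **Supportive analysis.** Keep the completers-only rate beside the main one.
- **Interim.** State one denominator, the first 10 who start radiotherapy, and say that early stoppers without a documented response count as not candidates.
- **Completion.** State whether a reduced-dose course, or one with oxaliplatin alone discontinued, counts as completed.
- **Accrual.** Edit 16.6 so that the 10% allowance covers only patients who never start.

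The cost is mainly wording; no visit or procedure is added. The real downside is a stricter rule. At a true 30% the chance of proceeding is about 0.58 rather than 0.67 to 0.70, and lower still if early stoppers who keep the organ are counted as failures for lack of documentation. The non-binding interim criterion is met somewhat more often: about 0.41 against 0.34 among completers at a true 20%, if 10% of non-completers keep the organ but none has a documented response. The investigators should accept these figures knowingly when they adopt the change.

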2.2 Secondary Objectives

1. To obtain prospective patient reported outcomes from an organ preservation approach for early stage rectal cancer.
2. To determine the incidence of any grade ≥ 3 toxicity during treatment.
3. To determine the incidence of post chemoradiotherapy grade ≥ 3 toxicity at 1 year
4. To determine quality of anorectal function at 1 year using the FACT-C questionnaire.

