16.5 Data Analysis

Demographic and clinical characteristics of the sample, as well as response, toxicity by grade and loss to follow up will be summarized using descriptive statistics. Incidence of grade 3 or higher acute toxicities (overall and gastrointestinal), incidence of organ preservation will be calculated. Descriptive statistics from the FACT-C questionnaire will be generated for evaluation of anorectal function at 1 year. The incidence of post radiotherapy grade 3 or higher toxicities at 1 year will also be provided.

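### Section 16.4 counts only treatment completers as evaluable and no section gives toxicity another denominator, so read literally the grade ≥3 incidences omit patients whose toxicity ended treatment

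*Combined protocol and SAP*

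**What the plan says.** Section 16.4 holds the only analysis-set rule in the document: "Patients who have completed all radiotherapy and chemotherapy will be considered evaluable for analysis". It continues: "Patients who are inevaluable for the primary endpoint will be replaced".

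Section 2.2 lists among the secondary objectives: "To determine the incidence of any grade ≥ 3 toxicity during treatment". A further objective covers grade ≥3 toxicity after chemoradiotherapy, at 1 year. For the analysis, 16.5 says: "Incidence of grade 3 or higher acute toxicities (overall and gastrointestinal), incidence of organ preservation will be calculated". It adds the 1-year incidence and a summary of toxicity by grade. It refers to the sample but does not define it, and it names no denominator for any toxicity figure.

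Other sections describe how toxicity can end treatment. Section 8: "If dose reduction is required after dose level -3, patient will discontinue protocol therapy". Section 8.2, on neutropenia: "If ANC < 1000 after 4 weeks, discontinue therapy". Section 8.2 has similar 4-week rules for platelets and diarrhea, and 7.3 says that grade 3/4 hypersensitivity to oxaliplatin requires therapy to be discontinued.

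Section 9.6 has grade ≥3 events collected for 1 year from the start of radiotherapy.

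**The concern.** A patient whose toxicity ends chemotherapy has not completed all chemotherapy. Under the literal wording of 16.4 that patient is not evaluable and is replaced by someone who counts only on completing. The analysis set is then selected on the outcome that objectives 2 and 3 are meant to measure, and the events most likely to be lost are the ones that made treatment impossible to finish.

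Tolerability is a real question here. Section 1 describes a precursor trial with 4 cycles of FOLFOX, while this trial plans 8, with an optional radiotherapy boost (6.1). Section 16.3 contains no toxicity stopping rule, so the incidences in 16.5 are the plan's main formal summary of safety.

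**Working it through.** **Inputs from the plan.** 20 evaluable patients, from 16.2: "if organ preservation is not possible in 30% of this initial cohort (6/20 patients), then the strategy will be abandoned". Accrual, from 16.6: "Assuming 10% inevaluable cases, the overall accrual will be 22 patients".

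**The plan's own figure.** 20 × (1 + 0.10) = 22, which reproduces the stated accrual. Dividing instead gives 20 / 0.9 = 22.2, or 23 after rounding up; the difference is immaterial here. The plan therefore expects 22 − 20 = 2 inevaluable patients.

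**Which stops are grade ≥3.** In the 8.2 table an ANC below 1000/mm³ is grade 3 or 4, so a stop for unresolved neutropenia always follows a grade ≥3 event. So does a stop for the grade 3/4 hypersensitivity described in 7.3. The other routes need not: platelets of 50,000–74,999/mm³ and grade 2 diarrhea are below grade 3 and can also lead to discontinuation if unresolved.

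**Effect on the incidence.** Let x be the completers with a grade ≥3 event, k the excluded patients, and j the excluded patients with such an event.

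- Completers only: x / 20
- All treated: (x + j) / (20 + k)
- Difference: [k / (20 + k)] × (j/k − x/20)

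The completers' figure is too low whenever toxicity is more frequent among the excluded patients than among completers. With k = 2 (from the plan, assuming both received some radiotherapy) and j = 2 (assumed worst case):

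| x (assumed) | Completers only | All treated | Difference (points) |
|---|---|---|---|
| 0 | 0/20 = 0% | 2/22 = 9.1% | 9.1 |
| 4 | 4/20 = 20% | 6/22 = 27.3% | 7.3 |
| 6 | 6/20 = 30% | 8/22 = 36.4% | 6.4 |
| 10 | 10/20 = 50% | 12/22 = 54.5% | 4.5 |

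Check for x = 6: (2/22) × (1 − 0.30) = 0.064.

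**Sensitivity to j, with x = 6.** j = 0 gives 6/22 = 27.3%, j = 1 gives 7/22 = 31.8%, and j = 2 gives 36.4%, against 30% among completers. If neither excluded patient had a grade ≥3 event, the completers' figure would be too high by 2.7 points.

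**Events that prevent completion.** Among completers the count is 0/20 whatever happens in the trial (exact 95% interval 0 to 16.8%). If both excluded patients had such an event, the all-treated figure is 2/22 = 9.1% (1.1 to 29.2%). This is a component of objective 2, not a separately planned endpoint.

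**Scale of sampling error.** The exact 95% interval is 11.9 to 54.3% for 6/20 and 17.2 to 59.3% for 8/22. The worst-case shift is small beside either interval, but it is systematic and avoidable.

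**The case against.** The strongest reply is that the completer rule was meant for response only. The sentence after the definition ties inevaluability to the primary endpoint, and the interim rule in 16.3, the other place where completion acts as a filter, also concerns that endpoint. Neither 2.2 nor 16.5 restricts toxicity to completers. This reading is plausible, and it means the plan cannot be said to have deliberately excluded these patients. But the qualifier governs replacement, the definition itself carries no limit, and no other text supplies a toxicity denominator. The collection rule in 9.6 and the safety reports in Section 14 ensure that events are seen; they do not say over whom the incidence is calculated.

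A reader might go on to infer more than the documents support:

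- *Fatal toxicity can never be counted.* Treatment takes up to about 2 + 4 + 16 = 22 weeks, or 26 with the permitted 4-week delay (6.1, 7.1), and events are collected for a year. A completer's later fatal toxicity would count. Only events that prevent completion are lost.
- *The protocol compels these stops, and all are grade ≥3.* Section 8.2 calls its modifications strongly recommended and leaves the final decision to the treating provider. Some stops follow grade 2 toxicity.
- *The bias must be downward.* The 10% inevaluable rate is not attributed to toxicity, and patients who withdraw without a grade ≥3 event would push the completers' rate up.
- *The decision on a successor trial rests on the toxicity figure.* Section 16.2 bases that decision on organ preservation alone.

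All four limits stand. They reduce the point but do not remove it.

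**Conclusion.** The point holds as a defect in the written analysis rule. Taken literally, 16.4 leaves patients who stopped for toxicity, or who died before completing treatment, out of objectives 2 and 3, and nothing elsewhere corrects this. The probable effect is to understate grade ≥3 incidence.

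At the plan's own 2 inevaluable patients, the understatement is at most 4.5 to 9.1 points for completer rates between 50% and 0%. That range assumes that both patients were treated and both had grade ≥3 toxicity; the documents give no event rates, so these are illustrations and not estimates. The one result that needs no assumed counts is that treatment-preventing toxicity is zero among completers by construction.

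Severity is moderate. The endpoints are descriptive, the trial is a pilot of about 20 patients, no go/no-go rule depends on toxicity, and severe events still reach the oversight bodies. The documents do not support treating this as a certain or a large bias.

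**What to change.** In 16.4, limit the completer definition to the primary endpoint (whether it suits that endpoint is a separate question). Add that all patients who receive at least one fraction of protocol radiotherapy are included in every toxicity analysis, whether or not they complete treatment or are replaced.

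In 16.5, use this denominator for each toxicity incidence, acute and at 1 year, and report how many patients stopped treatment because of toxicity. A completers-only figure can be kept as a labelled supplement if wanted.

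The cost is about one sentence in each section. As 9.6 is written, the data are already collected, and sample size, visits and treatment do not change. If an all-treated analysis was always intended, the edit only confirms it. The downside is that the reported toxicity rate may be less favourable.
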